#### Table 14.3.1.4.7 Treatment-related TEAEs to the Antiviral Control Arm by System Organ Class and Grouped Preferred Term (As Treated Population)

N = number of patients in analysis set; n = number of patients with data available; % = percentages are calculated based on N as the denominator; E = number of events.

TEAE = Treatment Emergent Adverse Event; NA= Not Applicable.

Note: TEAEs are events with start date on or after the date of first dose of any study drug or events with start date prior to the date of first dose of any study drug whose severity worsens on or after the date of first dose of any study drug. If the event started on the date of first dose of the first study drug administration however it is ticked as the event started prior to first study drug administration on Day 1 in the eCRF, it is not considered as a TEAE.

[a] Within a system organ class, patients may have reported more than one grouped preferred term. Patients are counted once for each grouped preferred term and each system organ class. [b] A treatment-related TEAE to the antiviral control arm is a TEAE considered by the investigator as related to the antiviral control arm (i.e., remdesivir or favipiravir) or with unknown/missing relationship to trial medication.

MedDRA version & meddra.

Reference: Listing 16.2.7.1

- Table template TAE002.
- Sort alphabetically by system organ class and descending grouped preferred term in the total column. Where grouped preferred terms tie these should be sorted alphabetically.
- Assign the version of MedDRA Dictionary to &meddra. macro variable as XX.X and update the version of MedDRA Dictionary used for coding as needed.

Table 14.3.1.4.8 Treatment-related TEAEs to the Antiviral C	Control Arm by Maximum Seve	erity, System Organ Class and	d Grouped Preferred Term (As
Treated Population)			

System Organ Class Grouped Preferred Term [a] Maximum Severity [b]	Plitidepsin 2.5mg (N=XXX) n (%) E	Plitidepsin 1.5mg (N=XXX) n (%) E	Plitidepsin Total (N=XXX) n (%) E	Control Arm (N=XXX) n (%) E
Number of Patients with at least one Treatment- related TEAEs to the Antiviral Control Arm [c]	NA	NA	NA	xxx (xxx.x) xxx
System Organ Class 1	NA	NA	NA	xxx (xxx.x) xxx
Grouped Preferred Term A	NA	NA	NA	xxx (xxx.x) xxx
Grade 1	NA	NA	NA	xxx (xxx.x) xxx
Grade 2	NA	NA	NA	xxx (xxx.x) xxx
Grade 3	NA	NA	NA	xxx (xxx.x) xxx
Grade 4	NA	NA	NA	xxx (xxx.x) xxx
Grade 5	NA	NA	NA	xxx (xxx.x) xxx
Grade >= 3	NA	NA	NA	xxx (xxx.x) xxx
etc.				

N = number of patients in analysis set; n = number of patients with data available; % = percentages are calculated based on N as the denominator; E = number of events.

TEAE = Treatment Emergent Adverse Event; NA= Not Applicable.

Note: TEAEs are events with start date on or after the date of first dose of any study drug or events with start date prior to the date of first dose of any study drug whose severity worsens on or after the date of first dose of any study drug. If the event started on the date of first dose of the first study drug administration however it is ticked as the event started prior to first study drug administration on Day 1 in the eCRF, it is not considered as a TEAE.

Adverse events were assigned severity grade using the Common Terminology Criteria for Adverse Events (CTCAE) Version 5.0.

[a] Within a system organ class, patients may have reported more than one grouped preferred term. Patients are counted once for each grouped preferred term and each system organ class.

[b] Patients with multiple events within a particular SOC or PT will be counted under the category of their most severe event within that SOC or PT.

[c] A treatment-related TEAE to the antiviral control arm is a TEAE considered by the investigator as related to the antiviral control arm (i.e., remdesivir or favipiravir) or with unknown/missing relationship to trial medication.

MedDRA version & meddra.

Reference: Listing 16.2.7.1

Programming notes (not part of the table):

• Table template TAE005.

• Sort alphabetically by system organ class and descending grouped preferred term in the total column. Where grouped preferred terms tie these should be sorted alphabetically.

- Assign the version of MedDRA Dictionary to & meddra. macro variable as XX.X and update the version of MedDRA Dictionary used for coding as needed.
- If a patient experienced more than one AE within the same SOC and PT, the AE with the maximum intensity should be counted for that SOC and PT.

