## 2.2 Overall Study Design

This is a randomised, multicentre, open-label, controlled Phase 3 study in which adults requiring hospital admission and oxygen supplementation for management of moderate COVID-19 infection will be randomised in 1:1:1 to:

- Plitidepsin 1.5 mg arm: Patients will receive plitidepsin 1.5 mg/day intravenous (IV) in addition to dexamethasone on days 1 to 3;
- Plitidepsin 2.5 mg arm: Patients will receive plitidepsin 2.5 mg/day IV in addition to dexamethasone on days 1 to 3;
- Control arm: Patients will receive dexamethasone IV on Days 1 to 3. Additionally, in accordance with local treatment guidelines, patients in this group may receive a regulatory-approved antiviral treatment.

The study allows up to a total cumulative dose of 60 mg of dexamethasone base (calculation of the total dose will also include corticosteroids administered within 72 hours before the start of the study treatment and dexamethasone administered as premedication).

Randomisation will be stratified for 3 factors:

- Geographical region (Europe vs. Rest of the World);
- Charlson Comorbidity Index (0-1 vs. >1); and
- Barthel Index (≥90 versus <90)

From treatment initiation on Day 1, patients will be followed in the hospital for at least 4 days and then through Day 31 ( $\pm$ 3 days) or resolution/stabilisation of treatment-related adverse events (AEs), treatment-emergent adverse events (TEAEs) of special interest, and serious adverse events (SAEs). Patients discharged from the hospital prior to Day 8 will return to an out-patient clinic for assessments on Days 8 ( $\pm$ 1 day), and 31 ( $\pm$ 3 days). On Day 15 ( $\pm$ 1 day), patients will be followed up in remote or on-site visit (Appendix 4).

An independent Data Monitoring Committee (IDMC) will oversee study conduct (safety and primary endpoint), including analysis of summary safety data as per the trial requirements.

The study is expected to randomise approximately 609 patients (203 in each arm) over a period of 20 months.

Patients will be considered to be on study from the signature of the informed consent form until the end of the follow-up period, that is, completion of the protocol-specified follow-up visit on Day 31 ( $\pm$ 3 days) or until resolution/ stabilisation of treatment-related AEs, TEAEs of special interest, and SAEs that occurred through Day 31, whichever is longer.

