# **5.2 As Treated Population**

All patients who received any exposure to any study drug (plitidepsin, dexamethasone, including for patients randomised to control arm, the regulatoryapproved antiviral treatments, such as, remdesivir or favipiravir) during the study will be part of the As Treated population. As Treated population will be analysed according to the treatment they actually received.

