Troponin increased, Troponin I increased, Troponin T increased, Acute respiratory failure, Apnoea, Dyspnoea exertional, Hyperventilation, Hypoventilation, Hypoxia, Tachypnoea, Diastolic hypertension, Hypovolaemic shock, Systolic hypertension.

- For Hepatobiliary disorders and Transaminase elevations:
  - Hepatobiliary disorders (SOC)
  - Liver function analyses (HLT)

The final list of terms that determine the AEs of special interest will be described in the 'Analysis Set Specification' document to ensure the latest MedDRA version is used for the analyses.

Summary tables of TEAEs by treatment group and overall plitidepsin will be produced for the As Treated population.

Assessment of AE severity will be based on the NCI-CTCAE, version 5.0.

A treatment-related TEAE to plitidepsin, dexamethasone or to the antiviral control arm, ie, the regulatory-approved antiviral for those patients randomised to the control arm (remdesivir or favipiravir), is an TEAE considered by the investigator as related to the corresponding study drug or with unknown/missing relationship to trial medication.

An overview table will summarize the number and percentage of patients with at least one of the following TEAEs, where patients with more than one TEAE in a particular category are counted only once in that category:

- Any TEAE;
- Any TEAE by severity;
- Any TEAE grade  $\geq$ 3;
- Any TEAE leading to discontinuation of any study drug;
- Any TEAE leading to death;
- Any treatment-related TEAE to any study drug;
- Any treatment-related TEAE grade  $\geq$ 3 to any study drug;
- Any treatment-related TEAE to any study drug leading to discontinuation of any study drug;
- Any treatment-related TEAE to any study drug leading to death;
- Any treatment-related TEAE to plitidepsin;
- Any treatment-related TEAE grade  $\geq$ 3 to plitidepsin;
- Any treatment-related TEAE to plitidepsin leading to discontinuation of any study drug;
- Any treatment-related TEAE to plitidepsin leading to death;

- Any treatment-related TEAE to dexamethasone;
- Any treatment-related TEAE grade  $\geq$ 3 to dexamethasone;
- Any treatment-related TEAE to dexamethasone leading to discontinuation of any study drug;
- Any treatment-related TEAE to dexamethasone leading to death;
- Any treatment-related TEAE to antiviral control arm;
- Any treatment-related TEAE grade  $\geq$ 3 to antiviral control arm;
- Any treatment-related TEAE to antiviral control arm leading to discontinuation of any study drug;

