### Table 14.3.1.1 Summary of Exposure (As Treated Population)

N = number of patients in analysis set; n = number of patients with data available; % = percentages are calculated based on the number of patients with at least one infusion/dose administered as the denominator.

SD = Standard deviation; Q1 = 25th percentile; Q3 = 75th percentile; Min = Minimum; Max = Maximum; NA= Not Applicable.

[a] Duration is defined as (last dose date - first dose date + 1).

Reference: Listing 16.2.5.1 and 16.2.5.2

- Table template TLB004B.
- The displayed xxx do not reflect actual decimal precision. Please follow Section 2.11 for rounding rules.
  The ">10 infusions/doses" category should only be presented if there are any cases in any treatment group.

Exposure	Plitidepsin (N=XX	1 2.5mg (X)	Plitidepsin (N=XX	1.5mg (X)		Control Arm (N=XXX)	
Statistic	Dexamethasone	Plitidepsin	Dexamethasone	Plitidepsin	Dexamethasone	Remdesivir	Favipiravir
Days where Total Amount was Administered							
n M (CD)	XXX	XXX	XXX	XXX	XXX	XXX	XXX
Mean (SD)	xx.x (xx.xx)	xx.x (xx.xx)	xx.x (xx.xx)	xx.x (xx.xx)	xx.x (xx.xx)	xx.x (xx.xx)	xx.x (xx.xx)
Median	XX.X	XX.X	XX.X	XX.X	XX.X	XX.X	XX.X
Q1, Q3	XX.X, XX.X	xx.x, xx.x	XX.X, XX.X	xx.x, xx.x	XX.X, XX.X	XX.X, XX.X	XX.X, XX.X
Min, Max	xx, xx	xx, xx	xx, xx	xx, xx	xx, xx	xx, xx	XX, XX
Days where Total Amount was Administered, n (%)							
0 day	xxx (xxx.x)	xxx (xxx.x)	xxx (xxx.x)	xxx (xxx.x)	xxx (xxx.x)	xxx (xxx.x)	xxx (xxx.x)
1 day	xxx (xxx.x)	xxx (xxx.x)	xxx (xxx.x)	xxx (xxx.x)	xxx (xxx.x)	xxx (xxx.x)	xxx (xxx.x)
2 days	xxx (xxx.x)	xxx (xxx.x)	xxx (xxx.x)	xxx (xxx.x)	xxx (xxx.x)	xxx (xxx.x)	xxx (xxx.x)
3 days	xxx (xxx.x)	xxx (xxx.x)	xxx (xxx.x)	xxx (xxx.x)	xxx (xxx.x)	xxx (xxx.x)	xxx (xxx.x)
4 days	xxx (xxx.x)	NA	xxx (xxx.x)	NA	xxx (xxx.x)	xxx (xxx.x)	xxx (xxx.x)
5 days	xxx (xxx.x)	NA	xxx (xxx.x)	NA	xxx (xxx.x)	xxx (xxx.x)	xxx (xxx.x)
6 days	xxx (xxx.x)	NA	xxx (xxx.x)	NA	xxx (xxx.x)	NA	NA
7 days	xxx (xxx.x)	NA	xxx (xxx.x)	NA	xxx (xxx.x)	NA	NA
8 days	xxx (xxx.x)	NA	xxx (xxx.x)	NA	xxx (xxx.x)	NA	NA
9 days	xxx (xxx.x)	NA	xxx (xxx.x)	NA	xxx (xxx.x)	NA	NA
10 days	xxx (xxx.x)	NA	xxx (xxx.x)	NA	xxx (xxx.x)	NA	NA
>10 days	xxx (xxx.x)	NA	xxx (xxx.x)	NA	xxx (xxx.x)	NA	NA

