### Table 14.3.1.2 Summary of Treatment-Emergent Adverse Events (TEAEs) (As Treated Population)

N = number of patients in analysis set; n = number of patients with data available; % = percentages are calculated based on N as the denominator.

TEAE = Treatment Emergent Adverse Event; NA= Not Applicable.

Note: TEAEs are events with start date on or after the date of first dose of any study drug or events with start date prior to the date of first dose of any study drug whose severity worsens on or after the date of first dose of any study drug. If the event started on the date of first dose of the first study drug administration however it is ticked as the event started prior to first study drug administration on Day 1 in the eCRF, it is not considered as a TEAE.

Adverse events were assigned severity grade using the Common Terminology Criteria for Adverse Events (CTCAE) Version 5.0.

[a] A treatment-related TEAE to any study drug, plitidepsin, dexamethasone or to the antiviral control arm, ie, the regulatory-approved antiviral for those patients randomised to the control arm (remdesivir or favipiravir), is an TEAE considered by the investigator as related to the corresponding study drug or with unknown/missing relationship to trial medication. MedDRA version & meddra.

Reference: Listing 16.2.7.1

- Table template TAE001.
- Assign the version of MedDRA Dictionary to & meddra. macro variable as XX.X and update the version of MedDRA Dictionary used for coding as needed.

Adverse Events Category Adverse Events Type	Plitidepsin 2.5mg (N=XXX)	Plitidepsin 1.5mg (N=XXX)	Plitidepsin Total (N=XXX)	Control Arm (N=XXX)
	n (%)	n (%)	n (%)	n (%)
Any treatment-related TEAE to the antiviral control arm [a]	NA	NA	NA	XXX (XXX X)
$Grade \ge 3$	NA	NA	NA	XXX (XXX.X)
Leading to discontinuation of any study drug	NA	NA	NA	xxx (xxx.x)
Leading to death	NA	NA	NA	xxx (xxx.x)
Any serious TEAE	xxx (xxx.x)	xxx (xxx.x)	xxx (xxx.x)	xxx (xxx.x)
$Grade \ge 3$	xxx (xxx.x)	xxx (xxx.x)	xxx (xxx.x)	xxx (xxx.x)
Leading to discontinuation of any study drug	xxx (xxx.x)	xxx (xxx.x)	xxx (xxx.x)	xxx (xxx.x)
Leading to death	xxx (xxx.x)	xxx (xxx.x)	xxx (xxx.x)	xxx (xxx.x)
Any serious treatment-related TEAE to any study drug [a]	xxx (xxx.x)	xxx (xxx.x)	xxx (xxx.x)	xxx (xxx.x)
$Grade \ge 3$	xxx (xxx.x)	xxx (xxx.x)	xxx (xxx.x)	xxx (xxx.x)
Any serious treatment-related TEAE to plitidepsin [a]	xxx (xxx.x)	xxx (xxx.x)	xxx (xxx.x)	NA

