• If a patient experienced more than one AE within the same SOC and PT, the AE with the maximum intensity should be counted for that SOC and PT.

Assign the version of MedDRA Dictionary to &meddra. macro variable as XX.X and update the version of MedDRA Dictionary used for coding as needed.

System Organ Class Grouped Preferred Term [a]	Plitidepsin 2.5mg (N=XXX) n (%) E	Plitidepsin 1.5mg (N=XXX) n (%) E	Plitidepsin Total (N=XXX) n (%) E	Control Arm (N=XXX) n (%) E
Number of Patients with at least one Treatment- related TEAEs to the Antiviral Control Arm [b]	NA	NA	NA	xxx (xxx.x) xxx
System Organ Class 1	NA	NA	NA	XXX (XXX.X) XXX
Grouped Preferred Term B	NA	NA	NA	xxx (xxx.x) xxx xxx (xxx.x) xxx
System Organ Class 2 Grouped Preferred Term C	NA NA	NA NA	NA NA	xxx (xxx.x) xxx xxx (xxx.x) xxx
etc.				× /

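### Antiviral-related adverse events are shown as a share of all controls although the antiviral is optional, and a missing causality entry can make a case of a control never given one

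*SAP*

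**What the plan says.** SAP Section 2.2 makes the antiviral optional: subject to local guidelines, "patients in this group may receive a regulatory-approved antiviral treatment". Section 5.2 defines the As Treated population broadly: "All patients who received any exposure to any study drug (plitidepsin, dexamethasone, including for patients randomised to control arm" and its antivirals. Controls who had dexamethasone only are therefore in the safety denominator.

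Tables 14.3.1.4.7 and 14.3.1.4.8 (antiviral-related TEAEs, without and with maximum severity) and Table 14.3.2.4.3 (serious ones) use a single control column, of the form "Control Arm (N=XXX) n (%) E". Their footnotes state that "percentages are calculated based on N as the denominator; E = number of events". The antiviral rows of the overview, Table 14.3.1.2, follow the same rule: "percentages are calculated based on N as the denominator". In all four the plitidepsin columns are set to not applicable.

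Section 7.7.2 defines a TEAE as treatment-related if it is "considered by the investigator as related to the corresponding study drug or with unknown/missing relationship to trial medication". Footnote [b] of Table 14.3.1.4.7 applies this to the antivirals: "related to the antiviral control arm (i.e., remdesivir or favipiravir) or with unknown/missing relationship to trial medication". Neither text requires that the patient received the drug.

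The exposure table, 14.3.1.1, handles the same drugs differently: "percentages are calculated based on the number of patients with at least one infusion/dose administered as the denominator".

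**The concern.** A row labelled as related to one drug is naturally read as that drug's reaction rate. Here the denominator includes patients who could not have reacted to the drug, because they never had it. The numerator can include such patients too, if their causality entry is blank or unknown. Setting the plitidepsin columns to not applicable respects exposure between arms, but nothing does so within the control arm.

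A stated safety objective (Section 2.1.3.2) covers adverse reactions against control, and Table 14.3.1.2 shows plitidepsin-related and antiviral-related rows in one display. Plitidepsin is the assigned treatment throughout its arms, whereas the antiviral depends on local practice. A reader who sets the two rows against each other is not comparing like quantities, and the gap depends on how many controls were given an antiviral.

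**Working it through.** The shells hold only placeholders, so there is no planned figure to reproduce. The check is of the definitions, followed by an illustration.

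**Formula.** Let f be the share of As Treated controls given an antiviral, r the share of those with an antiviral-related TEAE, and m the share of the remaining controls with a TEAE of unknown or missing relationship. The document gives none of the three. Following the shells:

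printed % = f × r + (1 − f) × m

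The rate among treated controls is r, so

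printed % − r = (1 − f) × (m − r)

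The printed figure is below r when m < r and above it when m > r.

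**Denominator alone (m = 0).** With r assumed at 10%:

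- f = 0.2: 0.2 × 10% = 2%
- f = 0.3: 0.3 × 10% = 3%
- f = 0.5: 0.5 × 10% = 5%
- f = 0.8: 0.8 × 10% = 8%

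**Both effects.** Assumptions: 203 controls (the planned arm size; Section 8 records that recruitment stopped early), r about 20%, and m either 0% or 5%, with counts rounded to whole patients.

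| f | Treated | Related among treated | Rate among treated | Printed, m = 0% | Untreated added, m = 5% | Printed, m = 5% |
|---|---|---|---|---|---|---|
| 10% | 20 | 4 | 20.0% | 4/203 = 2.0% | 9 | 13/203 = 6.4% |
| 25% | 51 | 10 | 19.6% | 10/203 = 4.9% | 8 | 18/203 = 8.9% |
| 50% | 102 | 20 | 19.6% | 20/203 = 9.9% | 5 | 25/203 = 12.3% |
| 75% | 152 | 30 | 19.7% | 30/203 = 14.8% | 3 | 33/203 = 16.3% |
| 90% | 183 | 37 | 20.2% | 37/203 = 18.2% | 1 | 38/203 = 18.7% |

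In the first row with m = 5%, 9 of the 13 patients counted would never have had an antiviral.

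**The sign can reverse.** In rows with few events, such as single terms or serious events, r may be small. With f = 50%, r = 1% and m = 2%, the printed figure is 0.5 × 1% + 0.5 × 2% = 1.5%, which is above r.

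**Can the plan identify the treated controls?** Yes. Table 14.3.1.1 counts patients dosed with each antiviral, Listing 16.2.5.1 carries start and end dates, and Tables 14.2.4.3.1 and 14.2.4.3.2 already split controls by antiviral receipt for efficacy.

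**The case against.** The percentage does what its footnote says. It is the share of control patients with a TEAE counted as antiviral-related, and for comparing arms as randomised the whole arm is a legitimate denominator. This stands: there is no arithmetic slip, and calling the figure simply wrong would go too far. It answers an arm-level question under a drug-level label. The row for events related to any study drug already covers the arm-level question.

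A reader might also infer that dilution makes plitidepsin look more toxic than the approved antivirals. The document does not support that. The missing-causality rule works the other way, its frequency and the share treated are unknown, and the plitidepsin-related and antiviral-related rows never share a filled column.

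Counting missing causality as related is an ordinary conservative rule, applied alike to all study drugs, and the eCRF might prevent a blank for a drug not given. No such event is shown to exist. But the SAP text does not rely on such a safeguard, and followed literally it allows the miscount.

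Finally, Section 7.7.2 plans no formal comparison of adverse events, and exposure counts and listings let a reader approximate the rate among treated controls. That limits the consequence. Table 14.3.1.1 gives remdesivir and favipiravir in separate columns, however, so the combined number treated is not printed.

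**Conclusion.** The point holds as one about definition and presentation in descriptive safety tables. Two things are established from the text. First, before any missing-causality additions, the printed percentage equals the rate among antiviral-treated controls multiplied by an unstated share treated. Second, the unknown/missing rule has no exposure condition, so a dexamethasone-only control can be counted as an antiviral-related case.

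The size is not determinable. In the 203-patient illustration the printed figure runs from 2.0% to 18.7% against about 20% among treated controls, but the share treated, the reaction rate and the missing-causality frequency are all assumed. The effects oppose each other and the net bias cannot be signed. No test and no primary conclusion depends on these tables. The correction is worth making because it is cheap and the needed data are already collected.

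**What to change.** 1. In Section 7.7.2 and the related-TEAE footnotes, treat an unknown or missing relationship as related to a given drug only if the patient received that drug at or before the event's onset or worsening.
2. For the antiviral rows of Table 14.3.1.2 and for Tables 14.3.1.4.7, 14.3.1.4.8 and 14.3.2.4.3, show the percentage on n1, the number of controls with at least one dose of remdesivir or favipiravir. Derive n1 from the exposure data, counting a patient who had both drugs once. Give it in a footnote or a separate column, so that two denominators do not sit under one heading. The arm-level percentage can stay beside it. Section 7.1 already allows a shell to set its own denominator.

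The cost is wording, one subset flag and a rerun of four outputs. As the database is locked, the revised outputs can be issued as labelled post-hoc tables, since the addendum's introduction allows tables to be added. The downside is that the percentages rest on fewer patients, selected by local guidelines and not by randomisation. A footnote should say that they are not a randomised comparison with the plitidepsin-related rates.

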#### Table 14.3.2.1.1 Listing of Deaths (As Treated Population)

Treatment Group: << Plitidepsin 2.5mg/Plitidepsin 1.5mg/Control Arm>>

Site ID - Patient ID	Age/Sex/Race [a]	Treatment Start Date Time (Day)/ Stop Date Time (Day) [b]/ Duration (Days)	Death Date (Day) [b]	Cause of Death	Relationship in any way to the Study Disease COVID-19	Fatal AE (Grouped Preferred Term)
XXXX-YYYYY	XX/X/X	DDMMMYYYY HH:MM (XX)/ DDMMMYYYY HH:MM (XX)/ XX	DDMMMYYYY (XX)	Adverse Event or Other: xxxxxxxxxx	Yes or No	XXXXXXXXXXXX
123-456789	45/M/W	19JUL2018 (1)/ 24JUL2018 (6)/ 6	24JUL2018 (6)	Adverse Event	No	Arrhythmia NOS
etc.						

[a] For sex, F = Female; M = Male. For race, AI = American Indian or Alaska native; A = Asian; BA = Black or African American; PI = Native Hawaiian or Other Pacific Islander; W = White; O = Other; UN = Unknown.

[b] Relative day to the start date of study treatment. MedDRA version & meddra.

Programming notes (not part of the listing):

- Listing template LAE003.
- Order by Site ID Patient ID.

• Assign the version of MedDRA Dictionary to &meddra. macro variable as XX.X and update the version of MedDRA Dictionary used for coding as needed.

